4.4.2. Supportive Secondary Endpoints

Unless otherwise specified, other secondary and exploratory efficacy analyses (not controlled for type 1 error) will be conducted using the EAS. Missing data will be imputed using LOCF or handled through MMRM without utilizing hybrid imputation technique.

Analyses for labs including 7-point self-monitored blood glucose, fasting insulin, and lipid parameters will be performed for both SI unit and CN unit.

4.4.2.1. Additional Secondary Efficacy Analyses

Table GPHL.4.3. Secondary Measures (Not Controlled for Type 1 Error)

Objective	Relative to the efficacy measure:	Analysis conducted in a manner similar to:	Additional Information
compare tirzepatide 10 mg and/or 15 mg QW with placebo at 72 weeks:	Mean change in body weight (kg) from randomization	MMRM model in Section 4.3.2.2	LSM estimates through 72 weeks will be plotted by study treatment.
	Mean change in BMI (kg/m ²) from randomization	MMRM model in Section 4.3.2.2	Baseline BMI (kg/m ²) will be used as a covariate. LSM estimates through 72 weeks will be plotted by study treatment.

Objective	Relative to the efficacy measure:	Analysis conducted in a manner similar to:	Additional Information
	Mean change in 7-point SMBG from randomization	MMRM model in Section 4.3.2.2	Baseline SMBG value will be used as a covariate and baseline HbA1c group ($\leq 8.5\%$, $> 8.5\%$) will be used as a fixed effect. In addition to the analyses on each of the 7-points, similar analyses will be done for the 2-hour morning, midday, and evening meal excursions, the mean of all meals 2-hour excursion, the mean of all 7-point measurements, the mean of all pre-meal measurements, and the mean of all 2-hour postprandial measurements.
	Mean change in fasting insulin from randomization	MMRM model in Section 4.3.2.2	Baseline fasting insulin will be used as a covariate. Estimated means through 72 weeks will be plotted by study treatment. Log transformation will be adopted for fasting insulin.
	Mean change in IWQOL-Lite-CT Physical Function composite (PF) score from randomization	ANCOVA model	Terms of treatment, stratification factors, and baseline IWQOL-Lite CT PF score will be used as a covariate. Missing data will be imputed using LOCF method.
	Mean change in SF-36v2 acute form physical functioning domain (PF) score from randomization	ANCOVA model	Same as above but using baseline SF-36 v2 acute PF score as a covariate.
	Mean change in EQ-5D-5L utility score and VAS score from randomization	ANCOVA model	Same as above but using baseline EQ-5D-5L utility score and VAS score as a covariate, respectively.
compare tirzepatide QW (all doses combined) with placebo at 72 weeks	Mean change in DBP (mmHg)	MMRM model in Section 4.3.2.2	All tirzepatide doses will be pooled together. LSM estimates through 72 weeks will be plotted by study treatment.

Objective	Relative to the efficacy measure:	Analysis conducted in a manner similar to:	Additional Information
	Mean change in LDL-C, VLDL-C, total-cholesterol, and free fatty acids from randomization	MMRM model in Section 4.3.2.2	All tirzepatide doses will be pooled together. Estimated means through 72 weeks will be plotted by study treatment. Log transformation will be adopted for lipids parameters.

Abbreviations: ANCOVA = analysis of covariance; BMI = body mass index; DBP = diastolic blood pressure; EQ-5D-5L = EuroQol-5 Dimension 5 Level; HbA1c = hemoglobin A1c; IWQOL-Lite-CT = Impact of Weight on Quality of Life-Lite-Clinical Trials Version; LDL-C = low-density lipoprotein cholesterol; LOCF = last observation carried forward; LSM = least squares mean; MMRM = mixed model for repeated measures; QW = once-weekly; SF-36v2 = Short Form 36 version 2 Health Survey version 2; SMBG = self-monitored blood glucose; VAS = Visual Analog Scale; VLDL-C = very low-density lipoprotein cholesterol.

Pharmacokinetic, pharmacodynamic, and PK/PD analyses are the responsibility of Lilly's PK/PD group, and therefore the detailed analysis plan will not be included in this SAP. A summary of tirzepatide concentration by time will be reported. Exposure-response analysis between tirzepatide concentration and safety, pharmacology, and efficacy may be performed using population PK and population PK/PD nonlinear mixed-effects modeling techniques implemented on NONMEM software. Additionally, the impact of intrinsic and extrinsic factors (such as age, weight, sex, renal, hepatic functions, and baseline histological scores) on PK and/or PD parameters may be evaluated. If ADA titers are detected in the immunogenicity samples, the impact of titers on tirzepatide PK and/or PD may be evaluated.

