9.4. Statistical Analyses

9.4.1. General Considerations

Statistical analysis of this study will be the responsibility of Lilly or its designee. Any change to the data analysis methods described in the protocol will require an amendment ONLY if it changes a principal feature of the protocol. Any other change to the data analysis methods described in the protocol, and the justification for making the change, will be described in the SAP or the clinical study report (CSR). Additional exploratory data analyses may be conducted as deemed appropriate.

Unless otherwise noted, all tests of treatment effects will be conducted at a 2-sided alpha level of 0.05, and the confidence interval will be given at a 2-sided 95% level. In statistical summaries and analyses, data will be analyzed as randomized.

Unless specified otherwise, efficacy analyses will be conducted using efficacy analysis set (EAS) and safety analyses will be conducted using safety analysis set (SS). Baseline is defined as the last nonmissing data collected prior to or at randomization.

Summary statistics for continuous measures will include sample size, mean, SD, median, minimum, and maximum. The analysis model to make comparisons among treatment groups relative to continuous measurements assessed over time will be a mixed model for repeated measures (MMRM), with terms of treatment, visit, treatment-by-visit interaction, stratification factors and baseline measurement as a covariate. An unstructured covariance structure will model relationship of within-patient errors.

Kaplan-Meier method will be used for estimation of cumulative event-free survival rates over time, and cox proportional hazards regression analysis will be used to compare hazard rates among treatments.

Summary statistics for categorical measures (including categorized continuous measures) will include sample size, frequency, and percentages. Logistic regression will be used to examine the treatment difference in binary efficacy outcomes if there is a need to adjust for covariates. Otherwise, Fisher's exact test will be used to examine the treatment difference in categorical outcomes.

Summary statistics for discrete count measures will include sample size, mean, SD, median, minimum, and maximum. The negative binomial regression model will be used for the treatment comparison of discrete count measures.

Other statistical methods may be used, as appropriate, and details will be described in the SAP.

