4.3.2.2. The Analysis Related to the Efficacy Estimand

The analysis related to efficacy estimand will be conducted utilizing data in the EAS.

For the mean percent body weight change from randomization, a MMRM will be conducted. REML will be used to obtain model parameter estimates and the Kenward-Roger option will be used to estimate the denominator degrees of freedom. The response variable of MMRM will be the percent change in body weight from baseline values obtained at each scheduled post baseline visit.

For the percentage of participants achieving at least 5% body weight reduction from randomization over time, a logistic regression model will be used with the response variable of achieving at least 5% body weight reduction (Yes or No) at 72-week visit, with missing value imputed using the predicted value from MMRM analysis followed by dichotomization.

For MMRM the independent variables of analysis model are treatment group, visit, treatment-by-visit interaction, stratification factors (type of AHM used at randomization, sex, and country/pooled country) as fixed effects, and baseline body weight as a covariate. An unstructured covariance structure will model relationship of within-patient errors. If this model fails to converge, the following variance covariance structures will be tested in order until convergence is achieved:

- heterogeneous Toeplitz
- heterogeneous first order autoregressive
- heterogeneous compound symmetry
- Toeplitz
- first order autoregressive, and
- compound symmetry.

The first covariance structure that converges will be used.

With the aid of the MMRM analysis, 2-sided 95% CIs for mean percent change in body weight from randomization to the 72-week visit for tirzepatide 10 mg and 15 mg compared to placebo will be derived and summarized. The resulting least squares mean (LSM) estimates of mean percent change in body weight from baseline will be plotted by visit and by study treatment.

With the aid of the logistic regression model, 2-sided 95% CI and odds ratio for percentage of participants achieving at least 5% body weight reduction from baseline to the 72-week visit between tirzepatide 10 mg and placebo, as well as tirzepatide 15 mg and placebo will be derived.

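### Table GPHL.4.3 names no own-baseline covariate for DBP, LDL-C, VLDL-C, total cholesterol and free fatty acids; read as written, these rows inherit baseline body weight

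*SAP*

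**What the plan says.** SAP 4.4.2.1, Table GPHL.4.3, lists secondary measures outside type I error control. Its model column is headed "Analysis conducted in a manner similar to". Two pooled-dose rows matter here, and both point to the MMRM of SAP 4.3.2.2:

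- DBP, with the added information "All tirzepatide doses will be pooled together. LSM estimates through 72 weeks will be plotted by study treatment".
- LDL-C, VLDL-C, total cholesterol and free fatty acids, with "All tirzepatide doses will be pooled together. Estimated means through 72 weeks will be plotted by study treatment" and a log transformation.

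Neither row names a baseline covariate. The MMRM they point to has treatment, visit, their interaction, and "stratification factors (type of AHM used at randomization, sex, and country/pooled country) as fixed effects, and baseline body weight as a covariate".

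Other rows of the same table do name their own baseline. For fasting insulin the entry is "Baseline fasting insulin will be used as a covariate"; BMI, 7-point SMBG and the patient-reported outcomes have equivalent entries. In Table GPHL.4.2 the HbA1c, waist and fasting glucose rows name their own baseline, and the rows for SBP and for triglycerides, HDL-C and non-HDL-C say outright that it takes the place of body weight.

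Protocol 9.4.1 sets the default MMRM for continuous measures with "stratification factors and baseline measurement as a covariate". SAP 4.9, which lists changes to protocol-planned analyses, mentions no change to this model.

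**The concern.** In Table GPHL.4.3 a silent row takes its covariate from Section 4.3.2.2. The absolute body weight row is silent and is right to be, because body weight is its own baseline. A programmer who applies that convention to the DBP and lipid rows would adjust a change in mmHg or in log lipid for kilograms and leave out the outcome's own starting value.

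That would produce odd pairs. SBP would be adjusted for baseline SBP, but DBP not for baseline DBP. Triglycerides and HDL-C would use their own baseline, but LDL-C from the same panel would not. DBP would also carry two different models in the report, because the safety MMRM of SAP 4.6, applied to vital signs in 4.6.3.4, uses the parameter's own baseline.

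At stake are the precision of five secondary estimates, their sensitivity to chance baseline differences, and the principle that the model should be fixed before unblinding and not chosen between two defensible readings.

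**Working it through.** **The plan's own figure.** The SAP gives no precision or power for these five outcomes. Its only power statement (Section 5) is above 90% for the co-primary endpoints. With 300 × (1 − 0.25) = 225 completers per arm, a difference of 11, SD 10 and two-sided alpha 0.025, the SE is 10 × √(2/225) = 0.943 and 11/0.943 = 11.7, against a critical value of 2.24. Power exceeds 99.9%, and likewise for 25% v 90% responders. The statement is reproduced but has no bearing on this point.

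**Inputs.** Pooled tirzepatide v placebo is 600 v 300 randomized (SAP Section 5), or 450 v 225 after the SAP's 25% dropout, 675 in all. Alpha is 0.05 two-sided (SAP 4.1). The correlation r between baseline and Week 72 is not in the documents, so it is an assumption, shown from 0.3 to 0.9.

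**Variance.** Take a common SD σ at both times, a single Week 72 contrast, and a body weight covariate that explains almost none of the change.

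- Without the own baseline, the variance of the change is 2σ²(1 − r).
- With the own baseline, the residual variance is σ²(1 − r²) = σ²(1 − r)(1 + r).
- The ratio is 2/(1 + r).

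The confidence interval widens by the square root of this ratio, and the effective sample size is 675 divided by it. An effect with 90% power under own-baseline adjustment lies 1.960 + 1.282 = 3.242 SEs from zero; under the literal reading its power is Φ(3.242/√ratio − 1.960).

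**Baseline imbalance.** Suppose the arms differ at baseline by D. The expected Week 72 difference is then the effect plus rD. The change score subtracts D, so the estimate is the effect − (1 − r)D. A one-SE imbalance is √(1/225 + 1/450) = 0.082 SD.

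| Assumed r | Variance ratio | CI wider by | Effective N of 675 | Power if 90% with own baseline | Shift from a one-SE imbalance (SD, opposite sign) |
|---|---|---|---|---|---|
| 0.3 | 1.54 | 24.0% | 439 | 74.3% | 0.057 |
| 0.5 | 1.33 | 15.5% | 506 | 80.2% | 0.041 |
| 0.7 | 1.18 | 8.5% | 574 | 84.8% | 0.024 |
| 0.9 | 1.05 | 2.6% | 641 | 88.5% | 0.008 |

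**Simulation check.** This used 2,000 trials per setting, 450 v 225, with body weight correlated 0 or 0.3 with the outcome's baseline. Variance ratios were 1.60 and 1.54 at r = 0.3, 1.30 and 1.30 at 0.5, and 1.13 and 1.16 at 0.7. Slopes on the imbalance were −0.73 and −0.63, −0.50 and −0.45, and −0.28 and −0.28; with own-baseline adjustment they were within about 0.03 of zero. Mean error was at most 0.0023 SD in either model, so both are unbiased over randomization. The value r = 0.9 was not simulated.

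**The case against.** The strongest reply is that the documents nowhere say that these outcomes are to be adjusted for body weight in place of their own baseline. The evidence is silence in two cells whose text concerns pooling, plotting and log transformation. The column heading asks for similarity to the Section 4.3.2.2 model, not identity, which leaves room for endpoint-specific adaptation. Protocol 9.4.1, the sibling rows and the safety MMRM all point to own-baseline adjustment as the intent. This stands: a reader might infer that the sponsor chose body weight, and the documents do not support that.

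A reader might also infer that the literal model would carry a chance baseline imbalance over in full, or bias the result. Neither follows. The change score already subtracts baseline, so only a (1 − r) share of the imbalance remains, with opposite sign, and the average over randomizations is correct.

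The size is also open to challenge. No document gives r, equal variances are assumed, and no document shows how much of the change body weight explains. At high r the loss is small. This too stands, which is why a range is given.

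What the reply does not remove is the gap. A silent row in this table does inherit body weight, as the absolute body weight row shows, so two models remain possible for five declared superiority comparisons.

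**Conclusion.** The point holds as a specification gap of minor severity. Read as written, the DBP and lipid/free fatty acid rows take baseline body weight as their only baseline covariate, unlike every comparable row and contrary to Protocol 9.4.1, with no change recorded in SAP 4.9.

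The cost arises only if the rows are implemented literally. It is then a variance between 1.05 and 1.54 times that of the own-baseline model for r between 0.9 and 0.3. This rests on the assumed r, on equal variances over time, on body weight explaining little of the change, and on a single-visit simplification of the MMRM.

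A reader might infer a threat to the trial's main conclusions, since LDL-C and total cholesterol were key secondary in the protocol. SAP 4.9 moved both to additional secondary, and SAP 2.1 applies no multiplicity control to that tier. No primary or key secondary result is affected.

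**What to change.** In both rows of Table GPHL.4.3, state that the outcome's own baseline is substituted for baseline body weight: baseline DBP in the DBP row, and the log-transformed baseline lipid or free fatty acid value in the other. The phrasing of the SBP row in Table GPHL.4.2 can be reused; it makes clear that body weight is replaced and not supplemented.

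The cost is one phrase in each of two rows and one model term. The Schedule of Activities already collects vital signs, the lipid panel and free fatty acids at Visit 3, so no new data are needed. The wording should be settled before unblinding.

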4.5. Exploratory Endpoints Analysis

Table GPHL.4.4. Exploratory Efficacy Analyses

Objective	Relative to the efficacy measure:	Analysis Conducted
compare tirzepatide 10 mg and/or 15 mg with placebo at 72 weeks	Percentage of participants achieving $\geq 25\%$ body weight reduction from randomization	logistic model in Section 4.3.2.2
compare tirzepatide 10 mg and/or 15 mg with placebo at 72 weeks	Percentage of participants whose BMI shifts between clinically relevant categories, ie, from baseline (<25, 25 to <30, 30 to <35, 35 to <40, ≥ 40) to postbaseline (<25, 25 to <30, 30 to <35, 35 to <40, ≥ 40)	Shift analysis will be conducted based on data from EAS.
compare tirzepatide 10 mg and/or 15 mg with placebo at 72 weeks	Mean change in health outcome measurements (Section 4.7.1)	Terms of treatment, stratification factors, and baseline measurement score will be used as a covariate. Missing data will be imputed using LOCF method.

Abbreviations: BMI = body mass index; EAS = Efficacy Analysis Set; LOCF = last observation carried forward.

In addition, for the following endpoints, analyses to assess the risk difference in proportions for an unconditional treatment effect (Ge et al. 2011) among each tirzepatide dose and placebo arm may be conducted:

- percentage of participants achieving at least 5% body weight reduction at 72 weeks
- percentage of participants achieving at least 10% body weight reduction at 72 weeks
- percentage of participants achieving at least 15% body weight reduction at 72 weeks
- percentage of participants achieving at least 20% body weight reduction at 72 weeks
- percentage of participants achieving at least 25% body weight reduction at 72 weeks

4.6. Safety Analyses

Unless specified otherwise, safety assessments will be based on the SS (Table GPHL.3.1). All events that occur between the first dose date of study drug and the end date of study participation will be included, regardless of the adherence to study drug.

The statistical assessment of homogeneity of the distribution of categorical safety responses between tirzepatide doses and placebo will be conducted using Fisher's exact test, unless specified otherwise.

For selected continuous safety parameters, the mean change from baseline versus placebo will be assessed via a MMRM using REML. Data from scheduled visits will be utilized for this analysis. Unless specified otherwise, the model will include country/pooled country, sex, type of AHM used at randomization, treatment group, visit and treatment-by-visit interaction as fixed effects, and baseline value of the safety parameter as a covariate. To model the covariance structure within participants, the unstructured covariance matrix will be used. If this model fails to converge, the covariance structures specified in Section 4.3.2.2 will be tested in order until convergence is met. If the data does not warrant the MMRM model, then ANCOVA model will be conducted.

For selected safety parameters, time-to-first-event analysis via the Cox-proportional hazards model may be conducted. Participants without the event will be censored at the end of study participation. For participants experiencing the event, the “time-to-first-event” will be the time (in weeks) from first dose to first occurrence of the event.

Where necessary, the rate of events will be analyzed using a generalized linear mixed-effects model assuming the number of events follow a negative binomial distribution and with treatment as a fixed effect. The logarithm of days during the active treatment period will be adjusted as an offset to account for possible unequal treatment duration of follow-up among participants.

4.6.1. Extent of Exposure

Summary of duration of follow-up (defined as time in days from date of randomization to the date of the last study visit) and/or duration on study treatment (defined as time in days from date of first dose of study treatment to date of last dose of study treatment plus 7 days) will be provided by treatment group using data from SS.

For the summary of duration on study and study treatment, the frequency and percentage of participants falling into the following range will be summarized by planned treatment group as well:

- >0
- ≥ 4 weeks
- ≥ 8 weeks
- ≥ 12 weeks
- ≥ 16 weeks
- ≥ 20 weeks
- ≥ 24 weeks
- ≥ 36 weeks
- ≥ 48 weeks
- ≥ 52 weeks
- ≥ 72 weeks

In addition, the frequency and percentages of participants falling into the following exposure ranges for study and study treatment may be summarized by planned treatment group:

- 0 weeks
- >0 to <4 weeks
- ≥ 4 to <8 weeks
- ≥ 8 to <16 weeks
- ≥ 16 to <24 weeks
- ≥ 24 to <36 weeks
- ≥ 36 to <48 weeks
- ≥ 48 to <52 weeks
- ≥ 52 to <72 weeks
- ≥ 72 weeks

No p-values will be reported in these summaries as they are intended to describe the study populations rather than test hypotheses about them.

4.6.2. Adverse Events

4.6.2.1. Treatment-Emergent Adverse Events

A TEAE is defined as an event that first occurred or worsened in severity after baseline. The MedDRA LLT will be used in the treatment-emergent derivation. The maximum severity for each LLT during the baseline period including ongoing medical history will be used as baseline severity. For events with a missing severity during the baseline period, it will be treated as “mild” in severity for determining treatment-emergence. Events with a missing severity during the postbaseline period will be treated as “severe” and treatment-emergence will be determined by comparing to baseline severity.

For events occurring on the day of first taking study medication, the CRF-collected information (eg, treatment emergent flag, start time of study treatment and event) will be used to determine whether the event was pre versus posttreatment, if available. If the relevant information is not available, then the events will be counted as posttreatment.

The counts and percentages of participants with TEAEs will be summarized by treatment using MedDRA PT nested within SOC. Statistical comparisons will be applied at both the SOC and PT levels. Events will be ordered by decreasing frequency within SOC. The SOC will be in alphabetical order. For events that are sex-specific, the denominator and computation of the percentage will include only participants from the given sex.

An overview of the number and percentage of participants who experienced a TEAE, SAE, death, discontinued from study treatment or study due to an AE, relationship to study drug will be summarized by treatment.

The counts and percentages of participants with TEAEs by maximum severity will be summarized by treatment using MedDRA PT. For each participant and TEAE, the maximum severity for the MedDRA PT is the maximum postbaseline severity observed from all associated LLTs mapping to the MedDRA PT. The maximum severity will be determined based on the nonmissing severities. If all severities are missing for the defined postbaseline period of interest, it will show as missing in the table.

